7.5. Follow-up Period

During the follow-up period, the continued safety of the subjects after discontinuation of study drug will be assessed.

7.5.1. Between Visits R3/A3/ET and F1

At the indicated study days, subjects whose Day 84 24-hr UFC result was \leq ULN should:

- Day 92 (R3/ET+7): Begin a 24-hr urine collection.
- Day 93 (R3/ET+8): Take the 24-hr urine collection to the study site, or a visiting nurse will assist with processing the sample and shipping it to the central laboratory, per subject preference.

7.5.2. Follow-up, Visit F1 (End-of-Study (EoS); End of Trial)

The target study day for the follow-up (EoS; end-of-trial) visit is 13 days after Visit R3/A3/ET. Only subjects whose most recent available 24-hr UFC is \leq ULN need to have a follow-up visit at the study site. All other subjects should be followed up via telephone to assess for new AEs and concomitant medications. Subjects who have ongoing AEs should be followed up as appropriate.

Subjects whose Day 92 24-hr UFC is \leq ULN should continue to be followed up and have morning serum ACTH and 24-hr UFC assessed every 2-4 weeks until their 24-hr UFC is $>$ ULN or until the Investigator and the Medical Monitor agree that the subject is stable.

At Visit F1 (EoS; end of trial), appropriate study site personnel should:

- Record adverse events and update medications.
- Record vital signs and weight.
- Perform a brief PE, with particular attention to assessing the subject for adrenal insufficiency.
- Collect blood samples for hematology, chemistry and hormones (11-DOC, 17-OHP, A, A4, ACTH, cortisol, DHEA, DHEAS, free T, P, renin, SHBG and total T).

- All blood hormone collections should be performed between 6-10 AM (06:00-10:00), as close to 8 AM (08:00) as practicable.
- Subjects need to be in a seated position for at least 15 minutes prior to collection of blood hormone levels so that renin and aldosterone levels are stable.
- If the subject is a woman of childbearing potential, collect a urine sample and perform a urine pregnancy test (preferred; or submit a serum or urine sample to a laboratory for pregnancy testing if required by your institution/IRB/EC).
- If the subject's most recent available 24-hr UFC result is \leq ULN, then:
 - Provide instructions regarding a 24-hr urine sample to be collected at home within 2-4 weeks after the previous sample.
 - Schedule the next study visit (unscheduled follow-up).
- At the completion of Visit F1 and all follow-ups, once the 24-hr UFC is $>$ ULN, discharge the subject from the study.

8. QUALITY CONTROL AND ASSURANCE

Before any subjects can be consented at an investigational site and prior to the conduct of any protocol-specific procedures, formal training of investigational site personnel will be conducted. The Investigator and all relevant investigational site staff are to be trained on all aspects of the study for which they are responsible. Site personnel may be trained at a formal initiation visit, at an Investigator's Meeting, or by another means as necessary. Monitoring and auditing procedures will be conducted in compliance with the International Council on Harmonisation (ICH) Guidelines for Good Clinical Practice (GCP). Onsite verification of the eCRFs for completeness and clarity, crosschecking with source documents and clarification of administrative matters will be performed on a regular basis. Monitoring visits will occur at regular intervals as noted in the monitoring plan. Through frequent communications with the investigational site, the CRA will ensure that the investigation is conducted according to protocol design and all applicable regulatory requirements. Additional details on the monitoring of this study are provided in Section 10.5. During the course of the study, investigational sites, the study database and all associated study documentation may be subject to quality assurance audits by the Sponsor, or their appointed representatives, on a planned or as-needed basis. In addition, representatives of associated regulatory bodies may conduct inspections at their discretion. The Investigator is responsible for ensuring direct access to all protocol-specific materials for the purpose of these activities.

9. STATISTICS

9.1. General Considerations

A Statistical Analysis Plan that includes a more technical and detailed description of the planned statistical analyses will be prepared prior to unblinding of the double-blind randomized withdrawal period of the study.

9.2. Sample Size

A sample size of 16 enrolled patients in the open-label dose-escalation period is sufficient per clinical considerations. No formal sample size calculation was performed.

9.3. Analysis Populations

Efficacy – The primary efficacy analysis population will be the Intent-to-Treat (ITT) population, based on all subjects who are randomized to the double-blind randomized withdrawal period and take at least one dose of double-blind study drug. The modified ITT (mITT) population, based on all subjects who complete at least 2 weeks in the double-blind randomized withdrawal period of the study, will be used for additional analyses. For efficacy analyses, subjects will be included in the treatment group to which they were randomized.

Safety – The safety population will include all treated subjects. Safety analyses will be based on the safety population. For the safety analyses for the double-blind randomized withdrawal period, subjects randomized to the placebo group who receive ATR-101 will be included in the treatment group of the active study drug that they received.

Pharmacokinetic – The PK population will include all subjects with measurable drug concentrations. PK analyses will be based on the PK population.

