3.1.3. Double-blind Randomized Withdrawal Period

The double-blind randomized withdrawal period will be up to 4 weeks in duration. A subject is eligible to enter the double-blind randomized withdrawal period if the mean of the Day 50 and Day 51 (“mean Day 50/51”) 24-hr UFCs meets at least one of the following randomization criteria:

- 24-hr UFC \leq ULN
- 24-hr UFC \leq 50% relative to the baseline value

Eligible subjects will be randomized in a 1:1 ratio to receive either ATR-101 at the same dose level being used at the completion of the open-label dose-escalation period (expected to be 1000 mg BID) or matching placebo. Subjects will continue in the double-blind randomized withdrawal period for 4 weeks or until their mean Day 64/65 24-hr UFC is $> 1.3 \times$ ULN and has also increased by $> 50\%$ relative to their mean Day 50/51 24-hr UFC, whichever comes first. Subjects who are not eligible to be randomized will enter the Additional Open-Label Dosing Period instead of the Double Blind Randomized Withdrawal Period (see below).

- **Study Days 57-70:** Twenty-four-hour UFCs will be collected on Days 64 and 65 (collections start on Days 64 and 65, respectively, and finish on Days 65 and 66, respectively). At the time of Visit R2 (Day 71), if the mean Day 64/65 24-hr UFC result is available and is $> 1.3 \times$ ULN, and has also increased by $> 50\%$ relative to the mean Day 50/51 24-hr UFC, the subject will complete the End-of-Treatment (EoT) visit (Visit R3) instead of Visit R2 and may then be started on another agent at the discretion of his or her physician. Otherwise, the subject will continue in the double-blind, randomized withdrawal period.
- **Study Days 71-85:** Twenty-four-hour UFCs will be collected on Days 79 and 84 (collections start on Days 79 and 84, respectively, and finish on Days 80 and 85, respectively). The EoT visit (Visit R3) will be completed on Day 85. Note: if the mean Day 64/65 24-hr UFC was not available at the time of Visit R2, but subsequently is found to meet criteria for study completion, the EoT visit should be performed as soon as practicable, rather than on Day 85. Additionally, if the Day 79 or Day 84 24-hr UFC is $>$ ULN, after completion of the EoT visit (Visit R3) the subject may begin treatment with another agent at the discretion of his or her physician.

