6.10.1. Efficacy Assessments

6.10.1.1. 24-Hour Urinary Free Cortisol

24-hr urine collections for assessment of UFC will be performed using the standard procedure (see Laboratory Manual). If a urine collection is suspected to be incomplete, a repeat 24-hr UFC may be performed with approval of the Medical Monitor.

Two collections will be done during the screening period, within 28 days prior to enrollment into the open-label dose-escalation period (Visit T1), and results reviewed for eligibility prior to enrollment. Subjects who require wash-out of medications should perform these collections AFTER wash-out.

During the Open-Label Dose-Escalation Period of the study, subjects will begin a 24-hr urine collection on Days 13, 14, 27, 28, 41, 42, 50, 51, and 56. In addition, subjects in the Double-Blind Randomized Withdrawal Period of the study will begin a 24-hr urine collection on Days 64, 65, 79, and 84; and subjects in the Additional Open-Label Dosing Period of the study will begin a 24-hr urine collection on Days 69, 70, 79, and 84. The collections that occur within 2 days before study visits should be brought to the corresponding study visit (along with any other samples that had not been previously submitted). For all other collections, when completed, a visiting nurse may assist with processing and shipping these 24-hr collections to the central laboratory, or the subject may submit them to the study site, per subject preference.

The mean of the Day 50 and the Day 51 (“mean Day 50/51”) 24-hr UFC results will be used by the Investigator to determine whether the subject meets criteria for randomization. For subjects in the Double-Blind Randomized Withdrawal Period of the study, the mean of the Day 64 and the Day 65 (“mean Day 64/65”) 24-hr UFC results, if available at the time of Visit R2, will be used by the Investigator to determine whether the subject should undergo Visit R3 rather than Visit R2. The Day 79 result and the Day 84 result will be used to make the initial determinations of whether the subject’s follow-up visit should be conducted at the study site or via telephone.

In addition, subjects whose Day 84 24-hr UFC is \leq ULN will collect an additional 24-hr urine sample for UFC on Day 92. This result, if available at the time the Day 98 visit is due, will also be used to determine whether the subject’s follow-up visit should be conducted at the study site or via telephone.

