7.3. Double-blind Randomized Withdrawal Period

Subjects whose mean Day 50/51 24-hr UFC level is \leq ULN or \leq 50% of their baseline value are eligible to enter the 4-week double-blind randomized withdrawal period. (Subjects who do not meet either of these randomization criteria will instead enter an additional 4-week open-label dosing period, described in Section 7.4.) Subjects entering the randomized withdrawal period will be randomized in a 1:1 ratio either to continue to receive ATR-101 at the dose at which they achieved mean Day 50/51 24-hr UFC \leq ULN or \leq 50% of their baseline value (expected to be 1000 mg BID), or matching placebo. Randomization will be stratified by baseline 24-hr UFC level (calculated as the mean of all 24-hr UFC levels obtained within the 28 days prior to enrollment into the open-label dose-escalation period). Subjects' 24-hr UFC levels will be followed during this period to determine the efficacy of ATR-101 in maintaining lowered levels compared to placebo.

During the double-blind randomized withdrawal period, the Investigator should assess the mean Day 64/65 24-hr UFC result as soon as possible to determine whether the subject meets criteria for study completion. Subjects are considered to have completed the study during the double-blind randomized withdrawal period when their mean Day 64/65 24-hr UFC level is $> 1.3 \times$ ULN and has also increased by $> 50\%$ relative to their mean Day 50/51 24-hr UFC level, or if they reach Visit R3 without meeting these criteria. When subjects are found to have completed the study, they should return to the study site immediately for Visit R3.

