7.3.2. Between Visits R1 and R2 and Between Visits R2 and R3/ET

On Days 64, 65, 79, and 84 during the double-blind randomized withdrawal period, subjects should:

- Collect an early morning saliva sample.
- Collect a late night saliva sample.
- Begin a 24-hr urine collection.

In addition, at the indicated study days during the double-blind randomized withdrawal period, subjects should:

- Days 66 and 80: Take the 24-hr urine collections and any collected saliva samples to the study site, or a visiting nurse will assist with processing the samples and shipping them to the central laboratory, per subject preference.
- Days 70 and 84 (the day prior to Visits R2 and R3/ET, respectively): Record the approximate time of the evening study drug dose.
- Day 85 (the day of Visit R3/ET): Take the Day 84 24-hr urine collection and any collected saliva samples (i.e., the Day 84 samples, and any other samples that were not previously submitted) to the study site.
- Day 84 (the evening prior to Visit R3/ET): Fast after 10 PM (22:00; water and maintenance medications allowed).

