ⁱ TWO early morning (30-45 minutes after awakening for the day) and TWO late night (10 PM - 12 AM; 22:00-00:00) saliva collections for salivary cortisol should be performed during the screening period within 28 days of enrollment into the open-label dose-escalation period and results reviewed for eligibility prior to enrollment. Subjects who require wash-out of medications should perform these collections AFTER wash-out. A visiting nurse may assist with processing and shipping the Screening and Day 41, 42, 50, 51, 64 (if applicable), 65 (if applicable), and 79 saliva collections to the central laboratory; or the subject may submit these to the study site for shipping to the central laboratory, per subject preference (all other collections should be brought by the subject to the next visit at the study site).

^j For subjects in the double-blind randomized withdrawal period, if the mean Day 64/65 24-hr UFC result is available prior to or at the time of R2, study completion assessment will be performed: if subjects are found to have met criteria for completing the study (i.e., 24-hr UFC is $>$ 1.3 \times ULN and has also increased by $>$ 50% relative to the mean Day 50/51 24-hr UFC), R3 will be conducted, rather than R2 (i.e., the subject will skip R2). If the mean Day 64/65 24-hr UFC does not meet criteria for completing the study, or the result is not available at the time of R2, the subject will proceed with R2.

^k Adverse events will be collected from the time the subject signs the informed consent form until the last study visit or 30 days after the last dose of study drug, whichever is later.

11-DOC, 11-deoxycorticosterone; 17-OHP, 17-hydroxyprogesterone; A, aldosterone; A4, androstenedione; ACTH, adrenocorticotrophic hormone; aPTT, activated partial thromboplastin time; demog, demographics; DHEA, dehydroepiandrosterone; DHEAS, dehydroepiandrosterone sulfate; ECG, electrocardiogram; ET, Early Termination; excl, exclusion; HbA1c, hemoglobin A1c; HBsAg, hepatitis B surface antigen; HCV, hepatitis C virus; HIV, human immunodeficiency virus; incl, inclusion; INR, international normalized ratio; P, progesterone; PE, physical examination; PK, pharmacokinetic(s) (samples); PT, prothrombin time; SHBG, sex hormone binding globulin; T, testosterone; tel, telephone visit; UFC, urinary free cortisol; ULN, upper limit of normal

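### Minor, supportive analyses only: the two-week mITT rule makes no exception for subjects who meet the Day 64/65 completion criterion, so a protocol-defined completer can fall out of the mITT because of a post-randomisation UFC result

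*Protocol*

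**What the plan says.** Section 9.3 makes the ITT (randomised, at least one double-blind dose) the primary efficacy population. For additional analyses it defines a second one: "The modified ITT (mITT) population, based on all subjects who complete at least 2 weeks in the double-blind randomized withdrawal period of the study". The Synopsis repeats this rule. Neither place says how to treat a subject whose double-blind period ends early under the protocol's own completion rule.

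Section 7.3 contains that rule. "Subjects are considered to have completed the study during the double-blind randomized withdrawal period when their mean Day 64/65 24-hr UFC level is" above 1.3 × ULN and also more than 50% above the mean Day 50/51 value. On timing it says that "the Investigator should assess the mean Day 64/65 24-hr UFC result as soon as possible" and that "When subjects are found to have completed the study, they should return to the study site immediately for Visit R3". Footnote j of Appendix 1 foresees a result before R2: "if the mean Day 64/65 24-hr UFC result is available prior to or at the time of R2, study completion assessment will be performed". Section 7.3.2 has the samples handed in soon after collection: "Days 66 and 80: Take the 24-hr urine collections and any collected saliva samples to the study site".

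Other sections tie the decision to R2. Section 3.1.3 (and the Synopsis) reads "At the time of Visit R2 (Day 71), if the mean Day 64/65 24-hr UFC result is available", with R3 then replacing R2. Section 6.10.1.1 says the result, "if available at the time of Visit R2, will be used by the Investigator to determine whether the subject should undergo Visit R3" in place of R2. Section 7.3.3 also makes the assessment at R2, and Table 7 puts the completion assessment in the Day 71 column.

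**The concern.** A subject who meets the Day 64/65 criterion has done what the protocol asked and is called a completer. If that subject attends R3 before two weeks have passed, the mITT rule removes the subject anyway. The cause of removal is a UFC value measured after randomisation, and UFC is the variable behind the primary endpoint. That is selection on outcome, not ordinary attrition.

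What is at stake is the reading of the mITT results beside the ITT results. If the subjects removed were mainly placebo non-responders, the mITT difference would shrink; if they were ATR-101 non-responders, it would grow. With at most 16 subjects randomised, a single exclusion is visible in the estimate.

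**Working it through.** The protocol gives no figure to reproduce here. Section 9.2 states 16 enrolled subjects and no formal sample size calculation. The check is day arithmetic, a responder limit and an illustration.

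**1. Time in the double-blind period.** Inputs: R1 on Day 57 (Section 7.3.1), R2 on Day 71 (Section 7.3.3), last of the two decisive collections finished on Day 66 (Section 3.1.3). Elapsed days = day of R3 − 57. The inclusive count adds 1.

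| R3 on Day | Elapsed | Inclusive | At least 14? |
|---|---|---|---|
| 67 | 10 | 11 | no |
| 68 | 11 | 12 | no |
| 69 | 12 | 13 | no |
| 70 | 13 | 14 | only if counted inclusively |
| 71 | 14 | 15 | yes |

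So the R2-based sections keep the subject in the mITT, with no margin on the elapsed count. The Section 7.3 wording allows an earlier R3 that takes the subject out.

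**2. What an early R3 requires.** From Day 66 to Day 71 is 5 days. Exclusion needs shipping, assay, review and the return visit to fit within 4 days of Day 66 (3 on the inclusive count). No laboratory turnaround is stated, so the frequency cannot be calculated.

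**3. Whether an early completer is a non-responder.** Completion needs a Day 64/65 mean above 1.3 × ULN, so the value is not normal. The other route to response needs UFC at or below 0.5 × baseline. Both can hold only if 0.5 × baseline > 1.3 × ULN, that is, baseline > 2.6 × ULN.

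- Baseline 1.3 to 2.6 × ULN (part of Stratum I): always a non-responder on that value. Example: baseline 2.4, Day 50/51 1.0, Day 64/65 1.6 × ULN. Rise 1.6/1.0 − 1 = 60.0%; reduction from baseline 1 − 1.6/2.4 = 33.3%.
- Baseline above 2.6 × ULN (the rest of Stratum I and all of Stratum II): either result is possible. Example of a responder: baseline 8, Day 50/51 1.5, Day 64/65 2.5 × ULN. Rise 2.5/1.5 − 1 = 66.7%; reduction 1 − 2.5/8 = 68.8%.

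**4. Illustration of size.** The protocol gives no response rates. Assumed: all ATR-101 and half of placebo subjects respond, one placebo early completer leaves the mITT, and the Day 64/65 mean is that subject's end-of-period value (the next scheduled collection is Day 79).

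| Per arm | ITT difference | mITT, non-responder lost | mITT, responder lost |
|---|---|---|---|
| 8 (all 16 randomised) | 8/8 − 4/8 = 50.0 | 8/8 − 4/7 = 42.9 (−7.1) | 8/8 − 3/7 = 57.1 (+7.1) |
| 4 (half randomised) | 4/4 − 2/4 = 50.0 | 4/4 − 2/3 = 33.3 (−16.7) | 4/4 − 1/3 = 66.7 (+16.7) |

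Direction also depends on the arm. With assumed 6/8 v 2/8 (50 points), dropping two placebo non-responders gives 6/8 − 2/6 = 41.7 points; dropping both ATR-101 non-responders gives 6/6 − 2/8 = 75 points. If nobody leaves before 14 days, this rule changes nothing.

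**The case against.** The strongest reply is that most of the protocol places the exit at Day 71, exactly where the two-week rule is satisfied. On that reading rule and exit fit together, and footnote j only says that R3 replaces R2, not that it is brought forward. The protocol also plans for slow results. It leaves the same 5 days between the end of the Day 51 collection (Day 52) and R1 (Day 57), and it provides for a Day 64/65 result still missing at R2. A late result means an exit after Day 71, with the subject kept. All of this stands, and it limits the reach of the point. It does not remove it, because Section 7.3 read as written permits an earlier R3 and the mITT rule has no exception.

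A reader might infer that the visit windows open a second route: Section 6.1 allows 2 days either way, so an R3 in the R2 slot on Day 69 would give 12 days. The documents do not support this. Section 6.1 applies only where nothing else is specified, and Section 7 and the Appendix 1 footnote specify plus 2 days for these visits.

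It is also fair that the illustrated shifts are what removing any one placebo subject would produce under those assumed rates, and that no power figure depends on them. The unseen SAP may refine how two weeks are counted, but the base rule is stated in the protocol itself.

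**Conclusion.** The point holds as a minor wording defect in a supportive population. On one of two conflicting descriptions of the R3 timing, a subject whom the protocol counts as a completer can be dropped from the mITT because of a post-randomisation UFC result. On the other description, or when the result is late, the subject stays in.

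Three stronger conclusions may tempt a reader, and the documents support none of them:

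- That early completers are routinely excluded: turnaround is not given and the frequency is unknown.
- That the mITT is biased in a known direction: early completers may come from either arm and, above a baseline of 2.6 × ULN, may be responders or non-responders.
- That the main result is at risk: the primary analysis uses the ITT, which keeps all these subjects.

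The 7.1 and 16.7 point shifts are illustrations that rest on the assumed rates, one exclusion from placebo, and arms of 8 or 4.

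**What to change.** Define the mITT as ITT subjects who either complete at least 2 weeks in the double-blind period, counted from the actual date of R1, or meet the Day 64/65 completion criterion. The mITT then differs from the ITT only by subjects who left before two weeks for other reasons. State whether the count is elapsed or inclusive, since Day 70 turns on it.

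The R3 timing in the Synopsis and Sections 3.1.3, 6.10.1.1 and 7.3.3 must be reconciled with Section 7.3; which timing is right is for the sponsor to settle. Aligning the window wording in Section 6.1 with Section 7 and Appendix 1 is a side clean-up.

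The cost is one clause in the protocol or SAP, with no change to data collection. It should be settled before unblinding, because a population rule changed afterwards invites challenge.
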